**Proprietary - Uncontrolled if Printed** 

## **Protocol Synopsis**

Protocol Number	PTC-0009
Title	Multicenter Pivotal Study of Neonate, Infant, and Young Child Vascular Stenoses Studying the Renata Minima Stent
Phase	Pivotal Study
Sponsor	Renata Medical
Investigational Device	Minima Stent
Study Objectives	To assess device performance and clinical safety and effectiveness of the Minima Stent in neonates, infants and young children requiring intervention for coarctation of the aorta or pulmonary artery stenosis who are indicated for treatment.
Study Design	Single arm, prospective, non-randomized, multi-center, open-label, Pivotal study.
Study Population	The study population will be comprised of patients with a clinically relevant pulmonary artery or aortic vascular stenosis who are indicated for treatment. For each treatment location (pulmonary artery or aortic vascular), a minimum of 10 patients will be treated.
Inclusion Criteria	
 
Inclusion criteria include:         
 
The subject's legally authorized representative has been informed of the nature of the clinical investigation, agrees to its provisions, and has provided written informed consent
 
Requiring treatment* of:

Exclusion Criteria	Exclusion criteria include:
	• Active bloodstream infection requiring antibiotic therapy within 3 days prior to stent implantation

	History of or active endocarditis (active treatment with antibiotics) within 180 days prior to stent implantation
	Aortic or pulmonary artery aneurysm in the location targeted for treatment
	Body weight < 1.5 kg
	Anatomic location of lesion judged by the investigator to not lend to the safe placement of a stent
	Target vessels larger or smaller than the Minima System balloon size ranges
	Known genetic syndrome known to be associated with vasculopathies such as but not limited to Williams syndrome, Loeys-Dietz syndrome, etc
	Clinical scenario requiring that more than one vessel needs stent implantation at the time of the trial procedure.
	Currently participating in an investigational drug study or another device study
	Major or progressive non-cardiac disease resulting in a life expectancy of less than six months
	Known hypersensitivity to aspirin or heparin and cannot be treated with other antiplatelet and/or antithrombotic medications
	Known hypersensitivity to cobalt-chromium or contrast media that cannot be adequately pre-medicated
Number of Subjects	Maximum of 42 US subjects
Number of Study Sites	8 US sites, with the possibility of additional Japanese and/or European Union sites pending the appropriate regulatory approvals.
Location of Study Sites	Children's Hospital Los Angeles
	Cedars Sinai Medical Center
	Seattle Children's Hospital
	Cincinnati Children's Hospital
	Boston Children's Hospital
	Nationwide Children's Hospital
	Le Bonheur Children's Hospital
Visit Schedule	Screening/baseline, discharge, 1 month, 3 months, 6 months, 12 months, and annually thereafter through 5 years

	Enrollment is expected to take up to 6 months and will be ongoing throughout the study.
Primary Efficacy Endpoint	
 
The primary efficacy endpoint will be assessed as the rate of clinical success, with the performance goal defined as a clinical success rate of greater than 77%.
 
Clinical success is defined as: 
 
Stenosis relief, defined by stent outer diameter ≥ 75% of the surrounding vessel immediately after deployment.
 
Freedom from open surgical intervention required to treat Minima Stent disfunction through 6 months.
 
Maintenance of stented vessel diameter ≥ 50% of post-implant diameter at 6 months; as measured using CT angiography and/or angiography.
 
 
 

Primary Safety Endpoint	The primary safety endpoint will be assessed as the percentage of cases with freedom from procedure- or device-related SAEs resulting in an event listed below, with the performance goal defined as greater than 78% of cases:  O Death O Cardiac arrest and/or emergency ECMO cannulation O Stroke O Limb loss O Vessel dissection of target lesion O Device thrombosis/occlusion O Cardiac perforation requiring percutaneous or open surgical intervention O Persistent cardiac arrhythmia requiring a pacemaker
Secondary Efficacy Endpoints	
 
Peak-to-peak pressure gradient (ventricle to arterial or arterial to arterial) < 20 mmHg after stent placement, when applicable.
 
Successful stent re-dilation (when indicated) at recatheterization, defined as an increase in the intra stent angiographic luminal diameter within 2mm of the adjacent native vessel diameter immediately after re-dilation.
 

Secondary Safety Endpoints	
 
Freedom from stent embolization or migration through 6 months.
 
Freedom from stent fracture that led to reintervention through 6 months
 
Freedom from non-elective Minima Stent explant at 90-days post re-dilation
 
Freedom from procedure- or device-related SAE during redilation that results in the following:         
 
Death
 
Cardiac arrest and/or emergency ECMO cannulation
 
Stroke
 
Limb loss
 
Vessel dissection of target lesion
 
 
 

	
 
Device thrombosis/occlusion
 
Cardiac perforation requiring percutaneous or open surgical intervention
 
Persistent cardiac arrhythmia requiring a pacemaker
 

Sample Size Considerations	The study intends to enroll a maximum of 42 subjects within the United States. For each treatment location (pulmonary artery or aortic vascular), a minimum of 10 patients will be treated. Additionally, no site will be permitted to enroll more than one third of the total subjects implanted in the study.  The chosen sample size is appropriate, as it allows for the analysis of each co-primary endpoint, with the appropriate power level. See
Statistical Analysis Methods	Descriptive statistics will be the primary analysis method. The proportion of subjects with device success will be calculated along with the associated 95% confidence interval. Other categorical endpoints will be described with percentages. Continuous variables will be presented as mean with the standard deviation or median. Time-to-event endpoints will be described with Kaplan Meier graphs as appropriate.  Other statistical analysis methods and graphing methods can be used in addition to those listed above, as appropriate.

EFS	Early Feasibility Study	
FDA	United States Food and Drug Administration	
GCP	Good Clinical Practice	
Н&Р	History and Physical Examination	
Het	Hematocrit	
Hgb	Hemoglobin	
HIPAA	Health Insurance Portability and Accountability	
	Act	
ICF	Informed Consent Form	
ICH	International Conference on Harmonization	
ICU	Intensive Care Unit	
IDE	Investigational Device Exemption	
INR	International normalized ratio	
IRB	Institutional Review Board	
LAR	Legally Authorized Representative	
PAS	Pulmonary Artery Stenosis	
RV	Right Ventricle	
RVOT	Right Ventricular Outflow Tract	
SAE	Serious Adverse Event	
SAP	Statistical Analysis Plan	
TTE	Transthoracic echocardiogram	
UADE	Unanticipated Adverse Device Effect	
WBC	White blood cell	

GROWTH: A Multicenter Pivotal Study of Neonatal, Infant, and Young Child Vascular Stenoses Studying the Renata Minima Stent DOC-0008 Rev. A 01/24/2024 Page 5 of 19

# 4 Introduction

#### 4.1 Preface

The use of endovascular stents in congenital heart disease was first described more than 30 years ago. Soon thereafter, pediatric cardiologists began exploring and successfully implanting stents in smaller children and infants. While these procedures have now been performed successfully for decades, there continue to be numerous important drawbacks. The current standard of care to treat pediatric and infant vascular stenosis is either open surgical plasty or off-label endovascular stent implantation. Despite the apparent benefits of stent placement, the use of stents in infants presents a unique challenge. Due to normal and expected somatic growth, when a stent is placed in an infant, there is an unavoidable risk of restenosis caused by the development of device-patient size mismatch. This risk can be largely mitigated by simple stent re-dilation over time, however, currently there are no stents available that are small enough to be safely placed in an infant vessel that can be re-dilated to adult vessel dimensions.

The Renata Minima stent was designed to address these issues by providing a lifetime stent solution for a neonate, infant, or young child with vascular stenosis through (1) the use of a specific delivery system and stent dimensions designed to safely navigate the vasculature of this unique population and (2) the design of a unique stent created to be re-dilatable to adult vessel dimensions and thereby provide the potential for stenosis relief over the course of a lifetime.

# 4.2 Scope of the analyses

These analyses will assess the efficacy and safety of the Renata Minima Stent System in comparison with a performance standard and will be included in the clinical study report.

# 5 Study Objectives and Endpoints

# 5.1 Study Objectives

The objective of the clinical investigation is to access device performance and the clinical safety and effectiveness of the Minima Stent in neonates, infants, and young children requiring intervention for coarctation of the aorta and/or pulmonary artery stenosis who are indicated for treatment.

# 5.2 Endpoints

Primary Efficacy Endpoint	The primary efficacy endpoint will be assessed as the rate of clinical success, with the performance goal defined as a clinical success rate of greater than 77%.
	
 
Clinical success is defined as:
 
Stenosis relief, defined by stent outer diameter ≥ 75% of the surrounding vessel immediately after deployment.
 
Freedom from open surgical intervention required to treat Minima Stent disfunction through 6 months.
 
Maintenance of stented vessel diameter ≥ 50% of post-implant diameter at 6 months; as measured using CT angiography and/or angiography.
 

Primary Safety Endpoint	
 
The primary safety endpoint will be assessed as the percentage of cases with freedom from procedure- or device-related SAEs resulting in an event listed below, with the performance goal defined as greater than 78% of cases: 
 
Death
 
Cardiac arrest and/or emergency ECMO cannulation
 
Stroke
 
Limb loss
 
Vessel dissection of target lesion
 
Device thrombosis/occlusion
 
Cardiac perforation requiring percutaneous or open surgical intervention
 
Persistent cardiac arrhythmia requiring a pacemaker
 
 
 
				
Secondary Efficacy Endpoints	
 
Peak-to-peak pressure gradient (ventricle to arterial or arterial to arterial) < 20 mmHg after stent placement, when applicable.
 
Successful stent re-dilation (when indicated) at recatheterization, defined as an increase in the intra stent angiographic luminal diameter within 2mm of the adjacent native vessel diameter immediately after re-dilation.
 
				
Secondary Safety Endpoints	
 
Freedom from stent embolization or migration through 6 months.
 
Freedom from stent fracture that led to reintervention through 6 months
 
Freedom from non-elective Minima Stent explant at 90-days post re-dilation
 
Freedom from procedure- or device-related SAE during re-dilation that results in the following:         
 
Death
 
Cardiac arrest and/or emergency ECMO cannulation
 
Stroke
 
Limb loss
 
Vessel dissection of target lesion
 
Cardiac perforation requiring percutaneous or open surgical intervention
 
Persistent cardiac arrhythmia requiring a pacemaker
 
 
 
				

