# **Exclusion Criteria**

Candidates will be excluded from the clinical investigation if any of the following are present:

- 1. Active bloodstream infection requiring antibiotic therapy within 7 days prior to stent implantation
- 2. History of or active endocarditis (active treatment with antibiotics) within 180 days prior to stent implantation
- 3. Aortic or pulmonary artery aneurysm in the location targeted for treatment
- 4. Body weight of < 1.5 kg
- 5. Anatomic location of lesion judged by the investigator to not lend to the safe placement of a stent
- 6. Target vessels larger or smaller than the Minima System balloon size ranges
- 7. Currently participating in an investigational drug study or another device study
- 8. Known genetic syndrome known to be associated with vasculopathies such as but not limited to Williams syndrome, Loeys-Dietz syndrome, etc
- 9. Clinical scenario requiring that more than one vessel needs stent implantation at the time of trial procedure.
- 10. Major or progressive non-cardiac disease resulting in a life expectancy of less than six months
- 11. Known hypersensitivity to aspirin or heparin and cannot be treated with other antiplatelet and/or antithrombotic medications
- 12. Known hypersensitivity to cobalt-chromium or contrast media that cannot be adequately pre-medicated

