#### 6.3 Study Assessments

Activity	Screening	Procedure	Post-Procedure	1 Month (±7days)	3 Months (±7days)	6 Months ±14 days)	12 Months (±30days)	Annually Years 2-5 (±45days)
Informed consent & HIPAA authorization	Х							
Inclusion/exclusion criteria assessment	Х							
Demographics	Х							
Medical history	Х							
Physical exam & vital signs	Х		X	X	X	X	X	X
WBC, Hgb, Hct, platelets	$X^1$							
Serum creatinine	$X^1$							
INR (if taking Warfarin)	Х							
Chest X-ray	Х		X	X	X	X		
Transthoracic echocardiogram	Х		X	X	X	X	X	Х
Concomitant medications	Х	X	X	X	X	X	X	X
Minima stent implantation		X						
Pre-and Post-implantation angiography and hemodynamic assessments (within procedure)		X						
Adverse events / Device deficiencies 		X	X	X	X	X	X	X
Concomitant procedures 	Х		X	X	X	X		
CT angiography						X 		

To reduce unnecessary blood draws from patients, blood work may be performed after successful completion of all other screening activities / in the catheterization lab prior to device introduction into the bloodstream.

 All AEs collected for 12 months post-transplant; after 12 months, see Section 8.2 for select AE reporting.

 See Section 8.8 for reporting of select concomitant medications/procedures.

 Catheter-based angiography can be performed in place of CT if clinically appropriate.

The table below defines the analysis time windows that correspond to the targeted visit time frame.

Visit (target day)	Lower bound (days)	Upper bound (days)
Month 1 (30)	2	60
Month 3 (90)	61	135
Month 6 (180)	136	270
Month 12 (360)	271	374

Analysis Time Windows

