#### 8.2 Analysis Populations

- 8.2.1 The All Treated (AT) population is defined as all subjects who signed informed consent, meet eligibility criteria and for whom a procedure was begun (defined as the initiation of vascular access).
- 8.2.2 The Attempted Implant (AI) population is defined as all AT subjects who continued to meet the eligibility criteria and had an attempted implant of the Minima stent. A subject is considered to have an attempted implant at the time in which the Minima Stent System is inserted into the subject.

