# **10 Efficacy Analyses**

### **10.1 Primary Efficacy Analysis**

The primary efficacy endpoint will be assessed as the rate of clinical success, with the performance goal defined as a clinical success rate of greater than 77%.

Clinical success is defined as:

- Stenosis relief, defined by stent outer diameter  $\geq$  75% of the surrounding vessel immediately after deployment.
- Freedom from open surgical intervention required to treat Minima Stent disfunction through 6 months.
- Maintenance of stented vessel diameter ≥ 50% of post-implant diameter at 6 months; as measured using CT angiography and/or angiography.

The AI patient population will be used to test the study hypothesis. The Clopper-Pearson method will be used to calculate the two-sided 95% confidence limits. If the lower limit of the resulting confidence interval exceeds 77%, then the null hypothesis will be rejected in favor of the alternative. This study hypothesis will be tested without imputation of missing data; however, additional sensitivity analyses will be performed to evaluate the effect of missing data on the study conclusions.

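### A child can score as a clinical success although a non-Minima stent was placed at the target lesion, because no efficacy component counts an added stent

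*SAP*

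**What the plan says.** The Protocol Synopsis, SAP 5.2 and SAP 10.1 define clinical success by the same three components:

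1. "Stenosis relief, defined by stent outer diameter ≥ 75% of the surrounding vessel immediately after deployment"
2. "Freedom from open surgical intervention required to treat Minima Stent disfunction through 6 months"
3. "Maintenance of stented vessel diameter ≥ 50% of post-implant diameter at 6 months; as measured using CT angiography and/or angiography"

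The analysis set is fixed in SAP 10.1: "The AI patient population will be used to test the study hypothesis". SAP 8.2.2 sets the entry point for that set: "A subject is considered to have an attempted implant at the time in which the Minima Stent System is inserted into the subject". Insertion of the system is therefore enough. A Minima Stent left in place is not required.

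The nearest eligibility rule is exclusion 9 in SAP 6.2: "Clinical scenario requiring that more than one vessel needs stent implantation at the time of trial procedure". It concerns a second vessel, not a second stent in the same lesion.

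SAP 4.1 describes the treatment background: "The current standard of care to treat pediatric and infant vascular stenosis is either open surgical plasty or off-label endovascular stent implantation".

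**The concern.** The study objective in SAP 5.1 is the performance, safety and effectiveness of the Minima Stent. The efficacy endpoint should therefore credit that device only with results it produced. Component 2 ties failure to the Minima Stent but is limited to open surgery. Component 3 measures the vessel, whichever device holds it open. A transcatheter rescue with a different stent is not a failure under any component.

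At stake is upward bias in a single-arm comparison with a fixed goal of 77%. No control group would share the bias, and the pass mark is a matter of a few children. If the scoring is not fixed in advance, it has to be settled case by case in an open-label study.

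**Working it through.** **Inputs.** From SAP 7: efficacy goal 77%, assumed success 97%; safety goal 22%, assumed event rate 4%; one-sided 2.5%; 36 subjects for both endpoints, 42 as the maximum. From SAP 10.1: pass if the lower limit of the two-sided 95% Clopper-Pearson interval exceeds 77%.

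**The plan's own figures reproduce.** With the normal approximation and the null variance under H0:

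- n = [(1.96·√(p0·q0) + 0.842·√(p1·q1)) / (p1 − p0)]². For efficacy, p0 = 0.77 and p1 = 0.97 give 23.4, so 24 (stated 24). For safety, 0.22 and 0.04 give 29.5, so 30 (stated 30).
- Power = Φ[(|p1 − p0|·√n − 1.96·√(p0·q0)) / √(p1·q1)]. At n=36 this gives efficacy 0.986 and safety 0.914. The product is 0.902 (stated 0.99, 0.91 and 0.90).

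The point does not dispute these figures.

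**How different cases score under the three components.**

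| Case | Component 1 | Component 2 | Component 3 | Result |
|---|---|---|---|---|
| Minima Stent reaches 75%; another stent added at the procedure or before the 6-month image; vessel adequate at 6 months | met | met (no open surgery) | met | success |
| Minima system inserted, Minima Stent not left in place, another stent used; vessel adequate at 6 months | met only if read literally | met | met if read literally | can be success |
| Minima Stent stays below 75%, then another stent added | not met on the ordinary reading | – | – | failure |

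**Do other rules catch the first two cases?** SAP 9.2 deals with surgical removal unrelated to Minima malfunction and with ineligible patients. SAP 13 deals with missing data, and a rescued child has complete data. The primary safety list in SAP 11.1 has no added-stent item. Migration, and fracture leading to reintervention, are secondary safety endpoints only (SAP 11.2). None of these changes the efficacy score.

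**Pass mark.** The Clopper-Pearson lower limit for x successes in n is the 2.5% quantile of Beta(x, n − x + 1).

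| n | Successes | Lower limit | Outcome |
|---|---|---|---|
| 36 | 33 | 77.5% | pass |
| 36 | 32 | 73.9% | fail |
| 42 | 38 | 77.4% | pass |
| 42 | 37 | 74.4% | fail |

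So 3 failures are allowed at n=36 and 4 at n=42. At that boundary, rescoring one child reverses the result.

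**Assumed range for the bias.** The documents give no rate of added stents. Suppose success from the Minima Stent alone is exactly 77%, so that the device does not meet the goal, and a further 2, 3 or 5 points of children score as successes through another stent. The counted failure rate f falls from 23% to 21%, 20% or 18%. The chance of a pass is P(X ≤ 3) with X ~ Bin(36, f), or P(X ≤ 4) with X ~ Bin(42, f):

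| Rescued (points) | Counted failure rate | n=36 | n=42 |
|---|---|---|---|
| 0 | 23% | 2.1% | 2.2% |
| 2 | 21% | 3.9% | 4.3% |
| 3 | 20% | 5.2% | 5.8% |
| 5 | 18% | 9.1% | 10.4% |

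Two points are enough to exceed the nominal one-sided 2.5%.

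**The case against.** The best defence is that the Minima Stent is understood throughout. SAP 4.2 and 5.1 confine the analyses and the objective to it, and the schedule in SAP 6.3 lists Minima implantation followed by post-implantation angiography. This stands for component 1. A reader might infer that any lesion rescued by another device counts as a success, including one where the Minima Stent stayed below 75%. The documents do not support that, because such a child already fails component 1 on the ordinary reading. The defence does not reach a Minima Stent that met 75% and was then supplemented.

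A reader might also infer that the schedule fails to capture a bail-out, since "Concomitant procedures" has no mark in the Procedure column. That does not hold either. Angiography with hemodynamics, and adverse events / device deficiencies, are both marked at Procedure, so an added stent should be visible. The row's footnote points to a Section 8.8, but section 8 of this SAP ends at 8.3. The reference is probably to protocol text not supplied, which may say more. A further mark would only be a convenience.

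Three other limits stand:

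- The plan is silent on added stents. It does not expressly score them as successes.
- The 2 to 5 points are assumptions, set at the boundary of the goal. That off-label stenting is a standard of care makes a second device plausible, but gives no frequency. SAP 4.1 also says that no available stent is both small enough for safe infant placement and re-dilatable to adult size.
- Whether an adjunct stent should be an efficacy failure is a choice about the composite. A second Minima Stent placed for a poor result is a bail-out too, so it should at least be reported.

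**Conclusion.** The point holds as a gap in the endpoint definition. Applied as written, the three components let a child pass although a non-Minima stent was placed at the target lesion. The clearest case is a Minima Stent that reached 75% and was later supplemented. The case of a Minima Stent not left in place depends on a literal reading of component 1.

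The size depends on a rate that the documents do not give. Under the assumed 2 to 5 points, with Minima-only success at 77%, the chance of a wrong pass is 3.9% to 9.1% at n=36 and 4.3% to 10.4% at n=42, against 2.1% and 2.2% with strict scoring. If no child receives another stent, nothing changes. Only the synopsis of the protocol was available, so a scoring rule elsewhere in the protocol cannot be excluded, but the SAP's endpoint and analysis sections contain none. It should be corrected because the remedy is cheap and one child can decide the test.

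**What to change.** In the synopsis, SAP 5.2 and SAP 10.1:

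- Name the Minima Stent in components 1 and 3.
- State that an attempted-implant subject with any non-Minima stent placed at the target lesion, at the index procedure or before the 6-month image, is scored as not a clinical success.
- Add a table of the number, type and reason for all stents placed at the target lesion, including additional Minima Stents.

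Marking the concomitant-procedures row at Procedure in SAP 6.3 is optional.

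This changes scoring and reporting only. It alters no treatment, visit or enrolment number. The cost is protocol and SAP wording, and a possibly slightly lower success rate. If the planning rate of 97% includes such children, exact efficacy power at n=36 would go from 0.978 to 0.896 with 2 points of added stents and to 0.675 with 5. At n=42 it would go from 0.992 to 0.943 and 0.757. The sponsor should therefore confirm what the 97% counts.
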